16 HOW SUPPLIED/STORAGE AND HANDLING

How Supplied

ARAKODA tablets contain 100 mg of tafenoquine (equivalent to 125.5 mg of tafenoquine succinate) and are dark pink, film-coated, capsule-shaped, and debossed with 'TQ100' on one side.

ARAKODA tablets are packed in polyamide aluminum and PVC formable laminate backed blisters with a peelable polyethylene terephthalate aluminum foil cover. Each blister card contains 8 tablets. Each carton contains 16 tablets (2 blister cards) (NDC 71475-257-01).

Storage

Store at 20°C to 25°C (68°F to 77°F). Temperature excursions are permitted to 15°C to 30°C (59°F to 86°F) [see USP Controlled Room Temperature]. Protect from moisture. Dispense only in the original carton.

17 PATIENT COUNSELING INFORMATION

Advise the patient to read the FDA-approved patient labeling (Medication Guide).

G6PD Testing and Hemolytic Anemia

Inform patients of the need for testing for G6PD deficiency before starting ARAKODA. Advise patients on the symptoms of hemolytic anemia and instruct them to seek medical advice promptly if such symptoms occur. Patients should contact their health care provider if they have darker lips or urine as these may be signs of hemolysis or methemoglobinemia [see *Warnings and Precautions (5.1)*].

Important Administration Instructions

- Advise patients to take ARAKODA with food.
- Advise patients to swallow the tablet whole and not to break, crush or chew it.
- Advise patients to complete the full course of ARAKODA including the loading dose, maintenance dose and terminal dose.

Potential Harm to the Fetus

Advise females of reproductive potential of the potential risk of ARAKODA to a fetus and to inform their healthcare provider of a known or suspected pregnancy [see *Warnings and Precautions (5.2) and Use in Specific Populations 8.1*].

Advise females of reproductive potential to avoid pregnancy or use effective contraception during treatment with ARAKODA and for 3 months after the final dose [see *Use in Specific Populations (8.3)*].

Lactation

Advise women with a G6PD-deficient infant, or if they do not know the G6PD status of their infant, not to breastfeed during treatment with ARAKODA and for 3 months after the final dose [*see Contraindication (4), Warnings and Precautions (5.2), Use in Specific Populations (8.2)*].

Methemoglobinemia

Inform patients that methemoglobinemia has occurred with ARAKODA. Advise patients on the symptoms of methemoglobinemia and instruct them to seek medical advice promptly if such symptoms occur [*see Warnings and Precautions (5.3)*].

Psychiatric Symptoms

Advise patients who experience hallucinations, delusions, or confused thinking while taking ARAKODA to seek medical attention as soon as possible. Other psychiatric symptoms, such as changes in mood, anxiety, insomnia, and nightmares, should be promptly evaluated by a medical professional if they last more than three days or severe [*see Warnings and Precautions (5.4)*].

Hypersensitivity Reactions

Inform patients that hypersensitivity reactions have occurred with ARAKODA. Advise patients on the symptoms of hypersensitivity reactions and instruct them to seek medical advice promptly if such symptoms occur [*see Warnings and Precautions (5.5)*].

Manufactured For:

60 Degrees Pharmaceuticals LLC,
[name],
[name]

1217a

MEDICATION GUIDE
ARAKODA (AIR-uh-KOH-duh)
(tafenoquine)
tablets, for oral use

What is the most important information I should know about ARAKODA?

ARAKODA can cause serious side effects including:

- **Breakdown of red blood cells (hemolytic anemia).** See “**Do not take ARAKODA if you:**”
ARAKODA can cause a breakdown of red blood cells (hemolysis) in people with glucose-6-phosphate dehydrogenase (G6PD) deficiency. Your healthcare provider will test you for G6PD deficiency before you start taking ARAKODA. Signs of hemolytic anemia may not happen right away (delayed reaction). Tell your healthcare provider or get emergency medical help right away if you develop signs of hemolytic anemia which include darkening of the urine, dizziness, confusion, feeling tired, light-headedness, or shortness of breath, pale skin or yellowing of the skin and whites of the eyes.
- **Decrease of oxygen in your blood caused by a certain type of abnormal red blood cell (methemoglobinemia).** Signs and symptoms of methemoglobinemia may not happen right away (delayed reaction). Get medical help right away if you have bluish coloring of the lips or skin, headache, fatigue, shortness of breath, or lack of energy.
- **Mental health (psychiatric) symptoms.** See “**Do not take ARAKODA if you:**”
Sleep problems, depression, anxiety and psychosis have happened while taking ARAKODA. Psychiatric symptoms may not happen right away (delayed reaction). Get emergency medical help right away if you develop hallucinations (seeing or hearing things that are really not there), delusions (false or strange thoughts or beliefs), or if you get confused or have problems thinking while taking ARAKODA. Call your healthcare provider if you develop changes in your mood, anxiety, trouble sleeping (insomnia), or nightmares for 3 days or longer while taking ARAKODA.
- ARAKODA can have other serious side effects. See “**What are the possible side effects of ARAKODA?**”

What is ARAKODA?

- ARAKODA is a prescription medicine used to help prevent malaria in people 18 years of age and older.
- Malaria is a serious disease of the blood that is spread by infected mosquitos.
- It is not known if ARAKODA is safe and effective in children.

Do not take ARAKODA if you:

- have G6PD deficiency.
- are breastfeeding a child known to have G6PD deficiency or breastfeeding a child that has not been tested for G6PD deficiency.
- have a history of psychotic disorders, or you currently have psychotic symptoms including hallucinations (seeing or hearing things that are not really there), delusions (false or strange thoughts or beliefs), or disorganized thinking or behavior.
- are allergic to tafenoquine, other 8-aminoquinolines, or any of the ingredients in ARAKODA. See the end of this Medication Guide for a complete list of ingredients in ARAKODA.

Before taking ARAKODA, tell your health care provider about all your medical conditions, including if you:

- have nicotinamide adenine dinucleotide (NADH) reductase deficiency. People with NADH reductase deficiency have a higher risk for methemoglobinemia if they take ARAKODA.
- have or have had mental health problems.
- are pregnant or plan to become pregnant. ARAKODA can harm an unborn baby who has G6PD deficiency.
 - You should not become pregnant during treatment with ARAKODA.
 - Females who are able to become pregnant should use effective birth control (contraception) during treatment with ARAKODA. Talk with your healthcare provider about birth control methods that may be right for you.
 - Your healthcare provider may suggest you take a pregnancy test before you start taking ARAKODA. Tell your healthcare provider right away if you become pregnant or think you might be pregnant during treatment with ARAKODA.
- are breastfeeding or plan to breastfeed. It is not known if ARAKODA passes into breast milk. See “**Do not take ARAKODA if you:**”
 - Your healthcare provider should check your child for G6PD deficiency before you start breastfeeding.
 - If you know your child has G6PD deficiency, do not breastfeed during treatment with ARAKODA and for 3 months after your last dose of ARAKODA.

Tell your healthcare provider about all the medicines you take, including prescription and over-the-counter medicines, vitamins, and herbal supplements. ARAKODA and other medicines may affect each other causing side effects.

How should I take ARAKODA?

- Take ARAKODA exactly as your healthcare provider tells you to take it.
- ARAKODA is given as 2 tablets that you will take together as a single dose. Each ARAKODA tablet has 100 mg of tafenoquine.
- You will **start taking ARAKODA** 3 days before you travel to a malaria area.

- Take 2 tablets, 1 time **each day for 3 days**.
- You will **continue to take ARAKODA** while you are in the malaria area.
 - Take 2 tablets, 1 time **each week**.
 - Start taking this dose of ARAKODA **7 days after the last dose of ARAKODA** that you took before your travel to the malaria area.
- You will **take your last dose of ARAKODA** after you leave the malaria area.
 - Take 2 tablets.
 - Take this dose of ARAKODA **7 days after the last dose of ARAKODA** that you took while you were in the malaria area.
- Take ARAKODA tablets whole. **Do not** break, crush, or chew the tablets before swallowing.
- Take ARAKODA with food.
- **It is important that you take the full course of treatment with ARAKODA. Do not** stop taking ARAKODA without first talking to your healthcare provider because the medicine may not work as well to prevent malaria.
- If you miss 1 or 2 daily doses of ARAKODA before your travel to the malaria area:
 - **1 daily dose:** take 2 tablets (missed dose), and then continue to take your daily dose of ARAKODA until you have taken a total of 3 daily doses before your travel to the malaria area. Start taking your weekly doses of ARAKODA 1 week after your last daily dose.
 - **2 daily doses:** take 2 tablets (missed dose), 1 time **each day for 2 days in a row (consecutive days)** so that you have taken a total of 3 daily doses before your travel to the malaria area. Start taking your weekly doses of ARAKODA 1 week after your last daily dose.
- If you miss any weekly doses of ARAKODA while you are in the malaria area:
 - **1 weekly dose:** take 2 tablets, 1 time on any day up to the time of your next scheduled weekly dose.
 - **2 weekly doses:** take 2 tablets, 1 time on any day before your next scheduled weekly dose.
 - **3 or more weekly doses:** take 2 tablets, 1 time **each day for 2 days** up to the time of your next scheduled weekly dose.
- If you miss taking your last dose of ARAKODA 7 days after the last dose of ARAKODA you took while you were in the malaria area, take this last dose of ARAKODA as soon as you remember.

What are the possible side effects of ARAKODA?

ARAKODA may cause serious side effects, including:

- See “**What is the most important information I should know about ARAKODA?**”
- **Allergic (hypersensitivity) reactions.** See “**Do not take ARAKODA if you:**”

Allergic reactions can happen after you take ARAKODA. Signs and symptoms of an allergic reaction may not happen right away (delayed reaction). Get medical help right away if you have any signs or symptoms of an allergic reaction including:

- swelling of the face, lips, tongue or throat
- fainting and feeling lightheaded
- itching
- rash
- trouble breathing or wheezing
- hives
- vomiting

The most common side effects of ARAKODA include: diarrhea, headache, back pain, nausea, vomiting, dizziness, increased liver enzyme levels in your blood, motion sickness, insomnia, depression, abnormal dreams and anxiety.

Other side effects of ARAKODA include eye problems. Some people who take ARAKODA can have a problem with the cornea of the eye called vortex keratopathy. This problem can be seen during an eye exam. Vortex keratopathy does not cause vision problems and will usually go away after you stop taking ARAKODA.

These are not all the possible side effects of ARAKODA.

Call your doctor for medical advice about side effects. You may report side effects to FDA at [name].

You may also report side effects to Sixty Degrees Pharmaceuticals, LLC at [name].

How should I store ARAKODA?

- Store ARAKODA at room temperature between 68°F to 77°F (20°C to 25°C).
- Protect tablets from moisture.

Keep ARAKODA and all medicines out of the reach of children.

General information about the safe and effective use of ARAKODA.

Medicines are sometimes prescribed for purposes other than those listed in a Medication Guide. Do not use ARAKODA for a condition for which it was not prescribed. Do not give ARAKODA to other people, even if they have the same symptoms that you have. It may harm them.

You can ask your pharmacist or healthcare provider for information about ARAKODA that is written for health professionals.

What are the ingredients in ARAKODA?

Active ingredient: tafenoquine succinate

Inactive ingredients: microcrystalline cellulose, mannitol, and magnesium stearate. The tablet film-coating contains the following inactive ingredients: hypromellose, iron oxide red, titanium dioxide, and macrogol/polyethylene glycol.

Manufactured for:

Sixty Degrees Pharmaceuticals, LLC
[name]

For more information, go to <https://60degreespharma.com> or call [name].

This Medication Guide has been approved by the U.S. Food and Drug Administration

Issued: August 2018

(b) (4)

(b) (4)

(b) (4)

NDC: 71475-257-01

Do not use if seal is broken

 **Arakoda™**
(tafenoquine) tablets,
for oral use

100 mg

Lot: XXXXXXXX Exp: MM/YY 

 **Arakoda™**
(tafenoquine) tablets,
for oral use

100 mg

Lot: XXXXXXXX Exp: MM/YY 

 **Arakoda™**
(tafenoquine) tablets,
for oral use

100 mg

Lot: XXXXXXXX Exp: MM/YY 

 **Arakoda™**
(tafenoquine) tablets,
for oral use

100 mg

Lot: XXXXXXXX Exp: MM/YY 

 **Arakoda™**
(tafenoquine) tablets,
for oral use

100 mg

Lot: XXXXXXXX Exp: MM/YY 

 **Arakoda™**
(tafenoquine) tablets,
for oral use

100 mg

Lot: XXXXXXXX Exp: MM/YY 

 **Arakoda™**
(tafenoquine) tablets,
for oral use

100 mg

Lot: XXXXXXXX Exp: MM/YY 

15.2 Appendix B: Dyspnea and Cough Severity Scales

15.2.1 Rating of Perceived Dyspnea (RPD) Scale

Modified Borg Scale (MBS) during exercise or tasks. This scale allows you to rate the amount of shortness of breath you feel. The MBS goes from 0 to 10. A score of 0 means you have no shortness of breath at all ([Crisafulli 2010](#)).

Modified Borg Scale for Grading the Severity of Dyspnea

- 0 (Dyspnea) NONE
- 0.5 (Dyspnea) EXTREMELY MILD
- 1 (Dyspnea) VERY MILD
- 2 (Dyspnea) MILD
- 3 (Dyspnea) MODERATE
- 4 (Dyspnea) INTENSE
- 5 (Dyspnea) RATHER INTENSE
- 6
- 7 (Dyspnea) VERY INTENSE
- 8
- 9 (Dyspnea) ALMOST UNBEARABLE
- 10 (Dyspnea) UNBEARABLE

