⁵ After resting for 3 minutes the number of breaths will be taken over one minute.

⁶ The severity of shortness of breath will be reported by the patient using the Modified Borg Scale for Grading the Severity of Dyspnea shown in [Section 15.2.1](#).

⁷ The severity of coughing will be reported by the patient using the Cough Severity Scale shown in [Section 15.2.2](#).

⁸ Prior medications used in the 14 days prior to the start of screening will be recorded.

⁹ Hematology tests include: WBC count, absolute neutrophil count, RBC count hematocrit, hemoglobin, platelet count; C-reactive protein, INR, PT/PTT.

¹⁰ Clinical chemistry tests include: BUN, creatinine, ALT and AST.

¹¹ Study drug will either be dispensed in the clinic, if the patient has a clinic visit on Day 1, or will be delivered by same day courier service to the patient at home on Day 1, after final eligibility has been determined the patient is randomized.

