9.3 Treatment Period

9.3.1 Week 1/Day 1 through Week 1/Day 3 (± 1 day for self-administration of study drug) – In-home

On Day 1, eligible patients will either return to the clinic or may have a telemedicine visit. Continued eligibility will be reviewed, and if eligible, patients will be randomized and will receive and self-administer 200 mg TQ or matching placebo on Days 1, 2, 3 ± 1 day. If the patient has an in clinic visit, s/he will be given sufficient study drug for the entire study. If the Day 1 visit is a telemedicine visit, the randomized blinded study drug will be sent via courier to the patient. Patients will be provided with an eDiary application (loaded onto a device of their choosing). The patient will self-administer study drug with food (per the label instructions [[Section 15.1](#)]) and record compliance in the eDiary. Patients will be provided an oral thermometer to check and record their daily temperature and a home pulse oximeter to record their daily oxygen saturation. Patients will record respiration rate, temperature, COVID-19 clinical signs including presence and severity of cough, respiration rate and shortness of breath, doctor's office and emergency room visits, AEs, and concomitant medications in the eDiary.

They will also record study drug administrations in the diary to monitor compliance. Daily diary data will be automatically uploaded to the electronic data management system and will be reviewed daily by clinical staff. Patients will be contacted by telephone or videoconferencing by designated study personnel on a daily basis to review AEs for severity by asking an open ended question, check for use of concomitant medications and more details such as dose, frequency, indication, and route of administration, and if there are new or worsening signs and symptoms of COVID-19 disease. Telephone interviews will follow a script and information will be recorded in source documents. If a suspected SAE or worsening of signs and symptoms of COVID-19 are reported, a study physician will be contacted to determine if the patient needs additional support (clinic visit, medication, or emergency room visit). If the patient cannot be reached an individual from their emergency contact list will be contacted to determine if the patient has been hospitalized.

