12.4 Planned Safety Analyses

12.4.1 Adverse Events

AEs will be coded using the most recent version of the Medical Dictionary of Regulatory Activities (MedDRA) preferred terms and will be grouped by system, organ, and class (SOC) designation. The incidence of new COVID-19 symptoms not present at screening will be reported separately from other AEs including the maximum severity and time of maximum severity relative to the start of investigational product. The severity, frequency, and relationship of AEs to investigational product will be presented by preferred term by SOC grouping. Listings of each individual AE including start

date, stop date, severity, relationship, outcome, and duration will be provided. Each AE (based on preferred terminology) will be counted once only for a given patient. If the same AE occurred on multiple occasions, the highest severity and relationship to investigational product will be assumed. Thus, study participants are not counted multiple times in a given numerator in the calculation of frequencies for a specific AE.

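### The dyspnea scale's labels at scores 4 and 5 run against its numbers, so patients who answer by the words can have those two levels swapped; endpoints based on absence of dyspnea are unaffected

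*Combined protocol and SAP*

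**What the plan says.** Section 15.2.1 gives the scale. Its direction is set by the statement "A score of 0 means you have no shortness of breath at all", and the list ends at 10, labelled unbearable, so a higher score is worse. In the middle of the list the labels are, in order:

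- "3 (Dyspnea) MODERATE"
- "4 (Dyspnea) INTENSE"
- "5 (Dyspnea) RATHER INTENSE"
- 6, with no label
- "7 (Dyspnea) VERY INTENSE"

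This is a working instrument. Note 6 to Table 1 (Section 6.2) states: "The severity of shortness of breath will be reported by the patient using the Modified Borg Scale". Table 1 has the patient enter the result in the eDiary each day.

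The plan uses dyspnea in two ways.

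- **Absent or present.** Clinical recovery (Section 4.1) requires shortness of breath to be absent. The secondary Day 12 endpoint by individual symptom (Section 5.1.2) concerns presence, and the exploratory time to resolution (Section 5.1.3) concerns disappearance.
- **Graded.** Section 5.1.3 lists time to maximum severity of COVID-19 symptoms. Section 12.4.1 reports new COVID-19 symptoms "including the maximum severity and time of maximum severity". Clinical staff review the diary daily, and Section 9.3.1 says that if a suspected SAE or "worsening of signs and symptoms of COVID-19 are reported, a study physician will be contacted".

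**The concern.** A verbal rating scale orders patients correctly only if its words and its numbers rise together. Here *rather* softens *intense*, so someone reading the words would place the label at 5 below the label at 4. If dyspnea goes from rather intense to intense and the patient picks the matching words, the diary stores 5 and then 4, which looks like improvement.

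This is the only graded dyspnea measure in the plan and patients complete it at home, so nothing else in the data set would put the two levels back in order. At stake is the ordering of patients with more than moderate dyspnea wherever the analysis or the diary review uses the grade and not just its absence.

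**Working it through.** No sample size, power or alpha figure enters this point. The check is one of order, followed by a worked illustration.

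**Step 1: the labelled scores.** Section 15.2.1 attaches words to ten scores: 0, 0.5, 1, 2, 3, 4, 5, 7, 9 and 10. Scores 6 and 8 have none. Ten labelled scores give 10 − 1 = 9 adjacent steps.

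**Step 2: rank the words by ordinary English intensity.** None < extremely mild < very mild < mild < moderate < rather intense < intense < very intense < almost unbearable < unbearable.

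**Step 3: compare the two orders.** Eight of the nine steps rise in both number and words. One does not: from 4 to 5 the number rises and the words fall. No other section defines *rather intense* as the stronger term.

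**Step 4: effect on a patient who answers by the words.** Let the true level be the patient's place in the word order of Step 2, numbered by the printed scores. The true level is then 4 when dyspnea is rather intense and 5 when it is intense. Answering by the words swaps them: true 4 is stored as 5, and true 5 as 4. Every other level is stored as it is.

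**Step 5: illustration.** Take a course that starts at 0, climbs one labelled level per entry and then falls back. Entry 6 is level 4, entry 7 is level 5 and entry 8 is level 7.

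| True peak | True entries from entry 5 | Stored entries from entry 5 | True maximum (entry) | Stored maximum (first entry) |
|---|---|---|---|---|
| 4 | 3, 4, 3 | 3, 5, 3 | 4 (6) | 5 (6) |
| 5 | 3, 4, 5, 4, 3 | 3, 5, 4, 5, 3 | 5 (7) | 5 (6) |
| 7 | 3, 4, 5, 7, 5, 4, 3 | 3, 5, 4, 7, 4, 5, 3 | 7 (8) | 7 (8) |

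Patients with true peaks of 4 and 5 show the same maximum at the same entry. For the true peak of 5, the time to maximum is one entry too early, and the true step of +1 between entries 6 and 7 is stored as 4 − 5 = −1. For a peak of 7, neither the maximum nor its timing changes.

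**Step 6: effect on the absence-based endpoints.** Scores 4 and 5 are both non-zero, so under a cut at 0 both mean dyspnea is present, swapped or not. Clinical recovery, Day 12 presence of the symptom and time to resolution (read as time to absence) come out the same.

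**The case against.** The strongest reply is that the numbers protect the patient. The appendix presents a numbered 0 to 10 scale in ascending order, and 6 and 8 have no words, so the scale cannot be answered by words alone. A patient reading down the list sees 5 placed after 4 and before 7. The eDiary screen is not shown. All of this stands. It means the swap is possible, not that it is usual.

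It can also be said that the wording may come from the cited source, so that exchanging the labels would alter a published instrument. That cannot be settled from the documents, and it governs how the fix is framed.

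Two stronger readings are tempting but are not supported.

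- **A reader might infer that the reversal corrupts the safety table.** Section 12.4.1 does not say that its maximum severity is the dyspnea score, and the only severity grades defined for events (Section 10.1.2) are mild, moderate and severe. The table is affected only if it is built on this score.
- **A reader might infer that worsening patients would be missed.** No section ties physician contact to a change in the score. Through Day 11, daily calls ask about new or worsening symptoms, and respiratory rate and oxygen saturation are recorded as well (Sections 6.1 and 10.6.4). From Day 13 to Day 27 there is no routine daily call, but diary review continues (Section 9.4.2). A patient at 4 or 5 is in any case recorded above moderate.

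Finally, both arms are blinded and see the same labels, so there is no evident source of bias between them.

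**Conclusion.** The ordering defect is real and confined to one of nine steps. For a patient who answers by the words, it can swap levels 4 and 5. It may therefore blur graded severity data: the exploratory time to maximum severity, any maximum-severity summary of new symptoms that uses this score, and diary review. How far it reaches into the exploratory endpoint depends on how maximum severity is defined, which Section 12.3.2 leaves to the SAP. The primary endpoint, Day 12 symptom presence and time to resolution are unaffected.

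The number of patients misrecorded cannot be estimated. A reader might assume that 5% to 20% of the 250 mITT patients reach this range and count 0.05 × 250 = 12.5 to 0.20 × 250 = 50 as affected. The documents give no such share. The count would also include patients who answer by the number and patients whose peak is 7, whose maximum is stored correctly. It describes exposure to the wording, not misrecording.

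The conclusion rests on the ordinary meaning of *rather* and on some patients answering by the words. It is a minor point, worth correcting because the correction is cheap.

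**What to change.** Check the labels at 4 and 5 against the source cited for the scale in Section 15.2.1.

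- If they differ from the source, correct Section 15.2.1 and the eDiary so that the wording rises with the score.
- If the source carries the same wording, keep it and state on the form that a higher number always means worse shortness of breath.

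Leave the 0 to 10 numbers and the recovery cut at 0 unchanged, so that the primary analysis is untouched.

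The cost is a text edit in the appendix and the eDiary. The one small downside is that, if enrolment has started, diary entries made with the present labels must be flagged so that graded severity analyses can distinguish them.
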